### **Pre-specified Secondary analyses**

#### **Safety signals from the RTS,S/AS01 phase 3 studies**

The incidence of meningitis has been very low in the study cohort, with no events in the first three years of the trial. A 95% confidence interval for the incidence rate of meningitis among children vaccinated with RTS,S/AS01, over the whole intervention period, up to the age of five years, will be calculated.

The incidence of cerebral malaria among children vaccinated with RTS,S/AS01E will be investigated by comparing the RTS,S/AS01 groups with the SMC alone group, controlling for SMC status using an indicator variable. Cox regression will be used to obtain the hazard ratio and its 95% confidence interval over the whole intervention period, up to the age of five years.

The incidence of febrile convulsions not related to malaria or another obvious cause among children vaccinated with RTS,S/AS01 will be investigated as for cerebral malaria, i.e. by comparing the RTS,S groups with the SMC alone group, controlling for SMC status using an indicator variable. Cox regression will be used to obtain the hazard ratio and its 95% confidence interval over the whole intervention period, up to the age of five years. The excess cases per 1000 child-years at risk, based on the incidence rate differences will also be presented. The subset of febrile convulsions that occurred within 7 days of vaccination will also be analysed.

An exploratory analysis for data from the first three years of the trial found no evidence that RTS,S/AS01 increases mortality in girls. This will be repeated over the whole intervention period, up to the age of five years.

This was done by comparing the incidence of deaths using Cox regression, with an interaction between a dummy variable indicating receipt of RTS,S/AS01E and gender. The Wald test p-value for the interaction term will be used to assess evidence for effect modification. This model will also include a dummy variable for SMC to adjust for SMC receipt. This will enable the

female: male mortality ratio and its 95% confidence interval to be calculated separately for RTS,S/AS01E recipients, and non-recipients. We will use indicator variables to obtain the ratio of these ratios, with the 95% confidence interval. We will also present the mortality ratio for RTS,S recipients versus non-recipients separately for males and females. Since it is hypothesised that this effect may be age-dependent, we will also carry out these analyses restricted to the period after the first booster dose.

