### **2.4.1 Risks of receipt of RTS,S/AS01E or tetanus toxoid or tetanus/diphtheria vaccine**

Recipients of the investigational vaccine (RTS,S/AS01E) may experience pain and/or swelling at the injection site, fever, headache, fatigue, nausea, vomiting and/or abdominal pain, joint pain and/or muscle aches but these features are usually only mild. About 1:1,000 children have been reported to develop a febrile convulsion after receipt of RTS,S/AS01E. In the first three years of RTS,S/AS01E plus SMC trial only five children have experienced a febrile convulsion and it is not known if all these children had received RTS,S/AS01E. In the large Phase III study, MALARIA-055, an imbalance in meningitis cases of any etiology (i.e. including cases with confirmed etiology and cases with no etiology found), with no cluster in time-to-onset, was observed in children 5-17 months of age at first dose [3]. Potential immune-mediated disease (pIMD) is a theoretical concern with adjuvanted vaccines but no evidence of autoimmune disease caused by RTS,S/AS01 has been observed. Nonetheless, both meningitis and pIMDs will be monitored as AEs of specific interest for the duration of the study.

Vaccination with tetanus or tetanus/diphtheria toxoids may cause mild local and systemic reactions and anaphylaxis has been recorded as a very rare adverse event following administration of this vaccine. Some children in the extension study will receive five doses of tetanus or tetanus/diphtheria toxoids during their first five years of life. Administration of a fourth dose of tetanus or tetanus/diphtheria/pertussis vaccine at the age of approximately 18 months is recommended in some routine infant immunization programmes. There is less experience of administration of a fifth dose. However, tetanus toxoid is recommended at each pregnancy in low income countries and many women must have received at least five doses of tetanus toxoid without any reports of adverse events.

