### **5. STUDY RECRUITMENT, ENROLLMENT AND WITHDRAWAL**

#### **5.1 Participant inclusion criteria**

In order to be eligible to participate in this study, a child must have been enrolled in the initial phase of the trial of seasonal vaccination with the RTS,S/AS01E vaccine and their parents or guardian must have provided consent for their inclusion in the extension study.

A child who has reached the age of five years and who is currently enrolled in the trial but who is no longer eligible to receive either of the interventions will be followed until the end of the extension study on safety grounds and for evidence of "rebound" malaria.

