## **Inclusion criteria for the Extension study**

[figure not shown]
In order to be eligible to participate in the extension study, a child must have been enrolled in the initial phase of the trial of seasonal vaccination with the RTS,S/AS01E vaccine and their parents or guardian must have provided consent for their inclusion in the extension study.

As described above, children above the age of 5 years on 1st June 2021 were no longer eligible to receive either of the interventions, but were followed until the end of the extension study on safety grounds and to begin longer-term monitoring for any increased risk of malaria in the period after the interventions were no longer given.

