#### **A) Whole intervention period (all children).**

The primary analysis population will be the whole intervention period. This is the period starting from enrolment in April 2017 until the end of the intervention year in which children reached 5 years of age (31 March 2021 for *older children*, 31 March 2022 for *younger children*).

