### Per Protocol Analysis

As a secondary analysis, the primary outcome of clinical malaria will also be analysed per protocol (PP). The PP population will be defined separately for each year of the study. Children who were vaccinated at all scheduled vaccination contacts in a particular year (3 in 2017, 1 in each subsequent year) and who, in the same year, were also seen at the first SMC/SMC placebo contact each month (4 per year) will be considered as 'per protocol' for that year.

Children who attended for SMC administration but who did not receive SMC because they had malaria and were referred for treatment will be included in the per protocol analysis.

'Per protocol' is defined differently for the two interventions (vaccination and SMC). For vaccination, a child must have *received* all vaccination doses that year; for SMC a child must only have *attended* all SMC contacts that year. This difference is necessary because the primary outcome of the trial (clinical malaria) can result in a specific SMC dose being missed permanently, whereas if a child had malaria at the time of vaccination, catch-up was attempted later in the season. The per protocol conditions will be applied equally to all three groups, i.e. to be considered as per protocol, a child must have received all doses of vaccine AND attended all SMC contacts, irrespective of which of these were active and placebo.

All secondary outcomes will be analysed by modified intention to treat, as described above.

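### For older children the RTS,S safety-signal analyses stop a year before safety follow-up does, and meningitis is the one signal with no planned comparison against SMC alone

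*Combined protocol and SAP*

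**What the plan says.** The SAP section on safety signals from the RTS,S/AS01 phase 3 studies covers four signals. For meningitis it plans "A 95% confidence interval for the incidence rate of meningitis among children vaccinated with RTS,S/AS01, over the whole intervention period". Cerebral malaria and febrile convulsions are compared between the RTS,S groups and SMC alone by Cox regression with an SMC indicator. Mortality is modelled with an RTS,S-by-sex interaction. All four are analysed "over the whole intervention period, up to the age of five years".

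SAP period A runs "until the end of the intervention year in which children reached 5 years of age". Period A and the Modified Intention to Treat section both put that end at 31 March 2021 for children born before 1 June 2016, and at 31 March 2022 for the rest. The same censoring reaches deaths and hospital admissions, because "All secondary outcomes will be analysed by modified intention to treat, as described above".

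Other sections set a longer horizon:
- Protocol 5.1 says that a child past the fifth birthday "will be followed until the end of the extension study on safety grounds", and the SAP's extension inclusion criteria repeat this. The SAP note on age groups says that surveillance of these children is unchanged.
- Protocol 2.4.1 says that "both meningitis and pIMDs will be monitored as AEs of specific interest for the duration of the study".
- Protocol 4.2.2(e) counts serious adverse events and deaths whenever they occur in the study, with special mention of meningitis and cerebral malaria.
- The SAP section on Serious Adverse Events tabulates hospitalisations and deaths by arm and cause over the whole study. Protocol Appendix 2 (A.2) requires every meningitis case to be reported as an SAE.

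**The concern.** Stopping the clock when interventions stop suits efficacy. It suits vaccine safety less well. Protocol 2.4.1 reports that the phase 3 meningitis imbalance did not cluster at any particular time of onset, and the SAP itself raises the possibility that the mortality effect in girls depends on age. The omitted year contains the oldest ages observed in the trial and some of the longest time since first vaccination. A meningitis case or a death in an older child in September 2021 would appear in the SAE table but would enter no rate, interval or model in the pre-specified signal analyses.

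The meningitis signal in phase 3 was an excess over controls. A rate in RTS,S recipients alone, however precise, cannot show or exclude such an excess. It also fits poorly with the SAP's multiplicity section, which promises p-values and intervals for safety outcomes.

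**Working it through.** **1. The plan's own figure on this person-time.** The documents give no power or precision for any safety signal. The stated figure that uses the same person-time is the superiority power in protocol 10.2.
- Person-time: 20,625 / 3 = 6,875 child-years per group.
- Rates: 0.200 against 0.200 × 0.88 = 0.176.
- SE = √((0.200 + 0.176) / 6,875) = 0.007395, and 0.024 / 0.007395 = 3.245.
- Power at two-sided 5% = Φ(3.245 − 1.960) = 0.901, which reproduces the stated 90%.

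The two RTS,S groups therefore have 2 × 6,875 = 13,750 planned child-years up to the cut.

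**2. RTS,S time left out, 1 April 2021 to 31 March 2022.**
- Children in the extension (SAP, illustrative sample size): 2,410 + 2,624 = 5,034. Taking two thirds in the RTS,S arms gives 3,356.
- Attrition: about 5% a year (protocol 10.2; assumed to continue). The second-year factor is 0.95 × 0.975 = 0.926.
- Share of older children: 50 to 65%. The documents say slightly more than half, about 60% (protocol 7.6.9), and 3,860/5,920 = 65.2%.
- Low: 3,356 × 0.926 × 0.50 ≈ 1,554. High: 3,356 × 0.926 × 0.65 ≈ 2,021.
- Cross-check: the rebound calculation in protocol 10.3.4 assumes 800 child-years per group, so 2 × 800 = 1,600.

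**3. Share of all RTS,S child-years.**
- 1,554 / (13,750 + 1,554) = 10.2%
- 1,600 / (13,750 + 1,600) = 10.4%
- 2,021 / (13,750 + 2,021) = 12.8%

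**4. Effect on the meningitis limit.** The exact Poisson upper limit of a two-sided 95% interval with zero events is 3.689 / person-time.

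| RTS,S child-years | Upper limit per 1,000 |
|---|---|
| 13,750 (as planned) | 0.268 |
| 15,304 | 0.241 |
| 15,350 | 0.240 |
| 15,771 | 0.234 |

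With two events, the limit falls from 0.525 to 0.471 on 13,750 and 15,350 child-years.

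**5. What a meningitis comparison could show.** SMC alone has 6,875 child-years, so its zero-event limit is 3.689 / 6,875 = 0.537 per 1,000, or 3.689 / 7,675 = 0.481 with the extra 800. Person-time is 2:1. If every case fell in the RTS,S arms, the one-sided exact p-value would be (2/3)^k: 0.026 for k = 9 and 0.017 for k = 10, so ten cases are needed for p ≤ 0.025. The documents give no background rate. Assuming 0.05 to 0.2 per 1,000 and the planned person-time, exact one-sided 2.5% power is 0-1% for a rate ratio of 2, 0.2-46% for 5 and 11-97% for 10.

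**The case against.** Four points on the other side have weight.

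- **Visibility.** A reader might infer that events in older children after March 2021 go unreported, or that meningitis cannot be seen by arm. The documents do not support this. The SAE table with Appendix 2 yields meningitis counts by arm, and protocol 8.1 has suspected meningitis and fatal events investigated and sent to the DSMB within 72 hours. What is missing is person-time, rates, intervals and a planned comparison. The SAP also does not say outright that the table covers older children after the cut.
- **Size.** A reader might put the loss at 24 to 32% (1,554 to 2,021 of about 6,381 extension RTS,S child-years, where 6,381 = 3,356 × (0.975 + 0.926)). That is the wrong base, because the signal analyses run from 2017. The subset of convulsions within 7 days of vaccination loses nothing, since older children were not vaccinated in 2021.
- **Deferred reporting.** Protocol 7.6.9 and the SAP's separate rebound analyses cover malaria and admission with severe malaria after interventions stop, so cerebral malaria is partly addressed. Neither commits to meningitis or to mortality by sex.
- **Confounding by stopped SMC.** Protocol 10.3.4 assumes that malaria incidence rises from 200 to 600 per 1,000 once SMC ends. A fixed SMC indicator would misdescribe that year, and rebound malaria could enter the safety hazard ratios. This is a good reason not to replace the planned analyses, but not a reason to omit a second one.

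A single rate is an understandable choice after three years without a meningitis case, and a formal test would have little power. Neither fact prevents reporting the control rate beside it.

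**Conclusion.** The point holds as a gap in the pre-specified safety analyses. For older children, all four signals, and deaths and admissions as secondary outcomes, stop on 31 March 2021 although safety follow-up continues, and meningitis lacks a planned comparison with SMC alone. The omitted time is about 1,550 to 2,020 RTS,S child-years, or 10 to 13% of the total, and the zero-event meningitis limit moves from about 0.27 to 0.23-0.24 per 1,000. These figures rest on the planned 6,875 child-years per group, equal arms, 5% annual loss and an older share of 50 to 65%. If more time accrues before the cut than planned, the share is smaller.

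The change is unlikely by itself to reverse a safety conclusion. Its value is that late events enter analyses fixed before unblinding, and that the meningitis rate can be read against a control.

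**What to change.** Keep the intervention-period safety analyses and efficacy periods A to E unchanged, and add to the SAP:

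1. A pre-specified second analysis of the four signals (except the 7-day convulsion subset), all-cause deaths and hospital admissions, from first vaccination to 31 March 2022 (the SAP's end of the extension) for all children by allocated group. Compare by randomised arm, or make the SMC indicator time-varying, because older children no longer received SMC.
2. Meningitis counts, person-time and exact 95% intervals in each of the three arms, with an exact rate difference or ratio for RTS,S against SMC alone where estimable, and a note that power is low.
3. A sentence confirming that the SAE table includes older children after March 2021.

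The cost is SAP wording and one more set of columns. Surveillance already covers these children, and the SAP releases the randomisation code only when the final database is ready, so the change can be made blind. The downside is that malaria arising off intervention enters the extended columns; the existing columns, shown alongside, allow it to be separated.

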### **7.2 The RTS,S/AS01E vaccine**

As described previously, the RTS,S/AS01E vaccine is a virus like particle (VLP) composed of the CSP protein of *P. falciparum* and HBsAg which is given with the adjuvant, AS01E. The vaccine may cause local side effects such as pain and redness at the site of vaccination in approximately 20% of recipients and minor systemic effects such as drowsiness and irritability are sometimes observed following vaccination. Fever post vaccination occurs in about 10% of children and febrile convulsions occurred in about 1% of

5-17 month old recipients enrolled in the phase 3 trial [3] but no persistent neurological effects were recorded. The main safety issues related to administration of RTS,S/AS01E during the phase 3 trial were a statistically significant increase in meningitis in children given the vaccine at the age of 5-17 months and an apparent increase in mortality in female vaccine recipients. However, during the first three years of the current trial, only five cases of febrile convulsion have been reported among the approximately 4,000 children who have received three priming and two booster doses of RTS,AS01 or control vaccine and no proven case of meningitis has been detected. Following a fifth dose of RTS,S/AS01E given in 2019, no increase in reported local or systemic side effects compared to previous vaccine doses was noted. To ensure that minor local and systemic adverse events, such as a reaction at the vaccine site or fever, are not enhanced following repeated doses of RTS,S, adverse events during the first seven days after vaccination will be recorded in a sub-set of children. SAEs will be recorded in all children throughout the period of the trial, as described below in Section 8 and Appendix 2.

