### **Secondary endpoints**

Secondary outcomes which are passively detected events, will be analysed in a similar way as for the primary outcome, i.e. estimating the hazard ratio using Cox regression with a robust standard error.

The prevalence ratio of secondary endpoints measured at the weekly survey (aggregated into three-month periods), and at end of season surveys (including *P. falciparum* parasitaemia, anaemia, etc) will be estimated using Poisson regression, with a robust standard error for the individual, as described in Zou, 2004 (10).

Linear regression models will be used to compare mean haemoglobin concentration between the groups.

Arithmetic mean parasite densities (including in the calculation samples which are parasite negatives, as having density of zero), will be compared between arms using Poisson regression with a robust standard error.

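### The planned Cox hazard ratios for febrile convulsions and cerebral malaria have no finite value if the combined arm or SMC alone has no event, and the SAP names no sparse-data method

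*Combined protocol and SAP*

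**What the plan says.** The SAP section on safety signals from the phase 3 studies treats four outcomes.

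- **Meningitis:** "with no events in the first three years of the trial"; only a rate with a 95% interval is planned.
- **Cerebral malaria:** RTS,S groups against SMC alone, with an SMC indicator; "Cox regression will be used to obtain the hazard ratio and its 95% confidence interval over the whole intervention period".
- **Febrile convulsions without malaria or another evident cause:** the same model, plus a rate difference per 1000 child-years. In addition, "The subset of febrile convulsions that occurred within 7 days of vaccination will also be analysed".
- **Deaths:** a Cox model with a vaccine-by-sex term, judged by a Wald p-value, also with an SMC indicator.

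The safety section does not say how the interval for a hazard ratio is built. The SAP's statistical methods for secondary endpoints specify, for passively detected events, "estimating the hazard ratio using Cox regression with a robust standard error". Cerebral malaria belongs there, because it is listed under hospital admissions due to malaria.

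On event numbers, protocol section 7.2 says "only five cases of febrile convulsion have been reported among the approximately 4,000 children", and section 2.4.1 says "only five children have experienced a febrile convulsion and it is not known if all these children had received" RTS,S. On frequency after RTS,S, section 2.4.1 has "About 1:1,000 children have been reported to develop a febrile convulsion after receipt of" the vaccine, while section 7.2 has "febrile convulsions occurred in about 1% of" phase 3 recipients aged 5-17 months.

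**The concern.** A Cox model needs at least one event on each side of the contrast. With so few events that may not happen, and the SAP does not say what would be reported instead. The question is whether this is a remote possibility or a realistic one, and whether the planned output would show plainly that it had failed. An unusable interval wastes the analysis. A falsely narrow one is worse, because a handful of events could look like proof of harm, or of protection, in a named safety signal.

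**Working it through.** The documents give no expected count or precision for these outcomes, so there is no planned figure to reproduce.

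**Inputs.** Five febrile convulsions in three years (protocol 2.4.1 and 7.2). Person-years: 6875 per group, 20,625 in all (protocol 10.2). Scaling five events to 20,625 person-years, with an assumed 15,000 to 17,000 in the first three years, gives 5 × 20,625/15,000 = 6.9 down to 5 × 20,625/17,000 = 6.1. I therefore use 5 and 7 events. I also use 3, purely as an assumption for the 7-day subset.

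**1. Which arms carry the vaccine effect.** The (RTS,S, SMC) indicators are (0,1) for SMC alone, (1,0) for RTS,S alone and (1,1) for combined. Two coefficients plus a free baseline fit three arm hazards exactly. The RTS,S coefficient is therefore log(hazard in combined / hazard in SMC alone), and RTS,S alone informs only the SMC coefficient. No event in either the combined arm or SMC alone leaves no finite estimate.

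**2. How likely that is.** Assume equal person-time, the same ratio r in both RTS,S arms and no SMC effect. Given N events, each falls in SMC alone with probability 1/(1+2r) and in combined with probability r/(1+2r). Then

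P(no finite HR) = (2r/(1+2r))^N + ((1+r)/(1+2r))^N − (r/(1+2r))^N.

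For N = 5 and r = 2: 0.8^5 + 0.6^5 − 0.4^5 = 0.328 + 0.078 − 0.010 = 0.395.

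| Events | r = 1 | r = 2 | r = 5 |
|---|---|---|---|
| 3 (assumed) | 56% | 66% | 82% |
| 5 | 26% | 40% | 65% |
| 7 | 12% | 24% | 52% |

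**3. What the software would print.** I used constructed data: 1,960 children per arm and 0, 2 and 3 events in SMC alone, RTS,S alone and combined.

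- *Model-based SE, country strata:* the hazard ratio was about 54,000 after 10 iterations and 3 × 10^11 after 20. The SE rose from 134 to over 300,000, and the interval ran from 0 to infinity.
- *Robust SE, refit without country strata:* as the hazard ratio ran past 59 million, the model-based SE was 4,436 but the robust SE stayed at 0.58. The printed interval would be 59 million divided and multiplied by exp(1.96 × 0.578) = 3.10, or about 19 million to 183 million.
- *Why:* the robust variance is about 1/3 from the three combined-arm events plus 1/1960 from the empty arm, and √(1/3 + 1/1960) = 0.578. The empty arm adds almost no uncertainty.
- *Other patterns:* 2, 3 and 0 events drive the ratio to zero; 0, 5 and 0 leave it unidentified; 1, 2 and 2 give a finite 2.0 (0.18 to 22.1).

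**4. Usable summaries for 3 events against 0, equal person-time.**

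- *Exact conditional:* p = 0.025^(1/3) = 0.292; lower limit p/(1−p) = 0.41; no upper limit.
- *Firth:* ratio 3.5/0.5 = 7.0. Values of p within 3.84/2 of the maximum of 3.5 log p + 0.5 log(1−p) give a penalised profile interval of about 0.68 to 940.
- *Unpenalised profile likelihood:* lower limit 1.12.

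The methods do not agree on whether 1 is excluded, so the choice must precede unblinding.

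**5. The rate difference.** 3/6.875 = 0.44 per 1000 child-years. With a variance that counts the empty arm as certain, SE = √3/6.875 = 0.25 and the interval is −0.06 to 0.93. Exact Poisson limits (0 events: upper 3.69; 3 events: 0.62 to 8.77) combined as 3 − √(2.38² + 3.69²) and 3 + 5.77, each divided by 6.875, give −0.20 to 1.28.

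**6. The two stated frequencies.** The SAP's example plot starts with 1927 + 1919 = 3846 children in the RTS,S arms. Read per child, 1 in 1,000 implies about 4 cases and 1% about 38.

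**The case against.** - **The SAP did adapt where it knew of a zero.** Meningitis is not put in a Cox model. This stands, and it shows the same care could be extended to the other signals.
- **Five events are documented for febrile convulsions only.** This stands. The documents do not support reading that count across to cerebral malaria or deaths; for these the point is a missing rule, not a predicted failure.
- **Wald intervals are not stated.** This stands in part. Wald is named only for the sex-interaction p-value. But an interval built from a robust standard error, as specified for secondary outcomes, is of that type. For febrile convulsions the robust error is an inference; a model-based one gives 0 to infinity instead.
- **Febrile convulsions also get a rate difference, and serious events are tabulated by group.** This stands, so the hazard ratio is not the only summary. The rate-difference method also uses a robust error, and this section plans no such measure for cerebral malaria.
- **The analysis covers the whole intervention period.** This stands: it is not an assessment of the sixth and seventh doses alone.

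A reader might infer that no event in SMC alone is the most likely result if the vaccine does harm. Zero is the modal count only if r exceeds N/2: above 2.5 with 5 events, above 3.5 with 7. At a doubling of risk its probability is 33% and 21%.

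**Conclusion.** The concern holds for the hazard ratios of febrile convulsions and, as a missing rule, of cerebral malaria. At 5 to 7 febrile convulsions, a non-finite hazard ratio is a realistic outcome even if the vaccine has no effect, and more likely still in the 7-day subset. The failure may not be visible, because a robust-error interval can look precise.

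The probabilities rest on the assumptions in step 2 and on the recorded count standing in for the SAP's endpoint. That endpoint is narrower in cause but covers more years, so the final number may be lower or higher.

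The documents do not show that all the safety signals will fail, or that the safety report would contain no valid interval at all. Nor can five events be called low or expected while the frequency after RTS,S is given as both 1 in 1,000 and about 1%, with the per-dose or per-child basis unclear. That is a separate inconsistency and does not change the choice of method.

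**What to change.** Before the randomisation code is released, add to the SAP's safety section:

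1. For febrile convulsions (all, and within 7 days) and cerebral malaria, one named method whenever any arm has few events, for example fewer than 10. Choose either a Firth-penalised Cox model with a profile-likelihood 95% interval, keeping the SMC indicator and country strata, or an exact conditional comparison of combined with SMC alone.
2. Do not pool the two RTS,S arms against SMC alone. That drops the SMC adjustment and changes the contrast. For cerebral malaria it would mix the vaccine effect with the absence of active SMC in the RTS,S-alone arm.
3. A small-sample interval in place of the robust error for the febrile-convulsion rate difference.
4. The same penalised, profile-likelihood approach for the sex-by-vaccine mortality interaction if any cell is sparse.
5. Event counts by arm beside every estimate.

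In the protocol, reconcile the two febrile-convulsion frequencies and say whether each is per dose or per child.

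The cost is wording and a little programming. Penalised estimates are shrunk slightly, and exact intervals are somewhat conservative and may have no upper limit.
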